20.0 Confidentiality*

A. Confidentiality of Study Data

Describe the local procedures for maintenance of confidentiality of study data and any records that will be reviewed for data collection.

*20.1 A. Where and how will all data and records be stored? Include information about: password protection, encryption, physical controls, authorization of access, and separation of identifiers and data, as applicable. Include physical (e.g. paper) **and** electronic files.*

Response: The file linking subjects' names to code will be in paper form and will be stored in a locked file cabinet inside PI's laboratory along with signed consent forms. The rest of the data will be stored in a password-protected computer in Furnas 809 which does not have an internet connection. Password will be disclosed only to individuals who are related to this project. After the mandatory 3 years of data retention, the questionnaire will be shredded. Only coded data will be reported in research papers, conference presentations, and participating research lab meetings.

20.2 A. How long will the data be stored?

Response: The file linking subjects' name to ID will be retained until the end of the study. It will be destroyed afterward. All data will be stored for at least 3 years in a password-protected folder regarding this project. After the mandatory 3 years of data retention, the data can be deleted from the password protected computer in Furnas 809

20.3 A. Who will have access to the data?

Response: Only researchers directly involved in the study will have access to this data. Access will only be available to those working on the project through password protection.

20.4 A. Who is responsible for receipt or transmission of the data?

Response: Only the PI ([name]) will be responsible for receipt or transmission of the data.

20.5 A. How will the data be transported?

Response: If data is transported, a password-protected hard drive will be used.

B. Confidentiality of Study Specimens

*Describe the local procedures for maintenance of confidentiality of **study specimens**.*

N/A: No specimens will be collected or analyzed in this research.
(*Skip to Section 19.0*)

20.6 *B. Where and how will all specimens be stored? Include information about: physical controls, authorization of access, and labeling of specimens, as applicable.*

Response:

20.7 *B. How long will the specimens be stored?*

Response:

20.8 *B. Who will have access to the specimens?*

Response:

20.9 *B. Who is responsible for receipt or transmission of the specimens?*

Response:

20.10 *B. How will the specimens be transported?*

Response:

21.0 **Provisions to Monitor the Data to Ensure the Safety of Subjects***

- N/A:** This study is not enrolling subjects, or is limited to records review procedures only. This section does not apply.

NOTE: Minimal risk studies may be required to monitor subject safety if the research procedures include procedures that present unique risks to subjects that require monitoring. Some examples include: exercising to exertion, or instruments that elicit suicidality or substance abuse behavior. In such cases, N/A is not an acceptable response.

21.1 *Describe the plan to periodically evaluate the data collected regarding both harms and benefits to determine whether subjects remain safe.*

Response: There will be extra personal in addition to the operator of the device to ensure the participant's safety. We will collect the response of the Borg exertion scale and ask the participants if there is any adverse effect after each session. A licensed physical therapist will monitor the participants walking patterns.

21.2 *Describe what data are reviewed, including safety data, untoward events, and efficacy data.*

Response: For each week, the cable tension data will be monitored to ensure the proper operation of the device. Safety harness will be also tested before each operation.

21.3 Describe any safety endpoints.

Response: For each training session, researchers are asked to record any adverse effects electronically.

21.4 Describe how the safety information will be collected (e.g., with case report forms, at study visits, by telephone calls with participants).

Response: We will ask the participants for any adverse effect/Borg exertion scale and all information will be recorded in a daily report form. And the cable tension data will be automatically saved in the computer that is controlling the device. Furthermore, the PI will have a weekly meeting with the team members to check for any adverse effects.

21.5 Describe the frequency of safety data collection.

Response: The cable tension data will be collected for every trial. Borg scale will be asked for every 10 minutes.

21.6 Describe who will review the safety data.

Response: PI will review the safety data by having a periodic meeting with the researcher.

21.7 Describe the frequency or periodicity of review of cumulative safety data.

Response: N/A

21.8 Describe the statistical tests for analyzing the safety data to determine whether harm is occurring.

Response: N/A

21.9 Describe any conditions that trigger an immediate suspension of the research.

Response: N/A

22.0 Withdrawal of Subjects*

N/A: This study is not enrolling subjects. This section does not apply.

22.1 *Describe anticipated circumstances under which subjects may be withdrawn from the research without their consent.*

Response: If the participant has difficulties walking for 6 minutes, we will automatically withdraw the participant as 6-min walk is included in one of our metrics. Though highly unlikely, if the participant cannot follow simple instructions to walk and stop he or she may be withdrawn from the study.

22.2 *Describe any procedures for orderly termination.*

NOTE: Examples may include return of study drug, exit interview with clinician. Include whether additional follow up is recommended for safety reasons for physical or emotional health.

Response: The PI will inform the participant of early termination. The participant will be compensated for the hours that he/she participated in the study.

22.3 *Describe procedures that will be followed when subjects withdraw from the research, including retention of already collected data, and partial withdrawal from procedures with continued data collection, as applicable.*

Response: We destroy all the data and records related to the specific participant whom we withdraw from the study.

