3.0 Scientific Endpoints*

2.1 Describe the scientific endpoint(s), the main result or occurrence under study.

*NOTE: Scientific endpoints are outcomes defined before the study begins to determine whether the objectives of the study have been met and to draw conclusions from the data. Include primary and secondary endpoints. Some example endpoints are: reduction of symptoms, improvement in quality of life, or survival. Your response should **not** be a date.*

Response: The two primary outcome measures will be the motion and the muscle activation data of the lower body during walking. Motion trajectory will be used to detect the changes in the kinematics and sEMG data will present the muscle activation of the participants. Ground reaction force, center of pressure, and center of mass will be evaluated with the instrumented insole and treadmill. Before the first and after the last training, participants will be evaluated for functional gait assessment, 6-min-walk, leg strength using dynamometer, international physical activity questionnaire (short form), usability questionnaire, and Modified Ashworth test by a physical therapist. This will show the kinematic and kinetic changes of the participant after the training.

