8.0 Inclusion and Exclusion Criteria*

8.1 *Describe the criteria that define who will be **included** in your final study sample.*

NOTE: This may be done in bullet point fashion.

Response: The inclusion criterion for the study is adults with cerebral palsy (18-65 years old) who can ambulate a distance of 100 feet with or without the use of assistive devices. However, they shouldn't need physical assistance from a caregiver while they walk 100 feet.

8.2 *Describe the criteria that define who will be **excluded** from your final study sample.*

NOTE: This may be done in bullet point fashion.

Response: Recruited participants will be excluded if they have severe Equinovarus foot or Genu recurvatum of the knee. Participants who had surgery within 6 months will be excluded. Individuals with pregnancy, lower limb prosthetics, severe respiratory problems such as chronic obstructive pulmonary disease, heart disease, a loss of sensation, uncontrolled blood pressure, a seizure disorder, severe arthritis will be excluded from this study.

8.3 *Indicate specifically whether you will include any of the following special populations in your study using the checkboxes below.*

NOTE: Members of special populations may not be targeted for enrollment in your study unless you indicate this in your inclusion criteria.

Response:

- Adults unable to consent
- Individuals who are not yet adults (infants, children, teenagers)
- Pregnant women
- Prisoners

8.4 *Indicate whether you will include non-English speaking individuals in your study. Provide justification if you will exclude non-English speaking individuals.*

*In order to meet one of the primary ethical principles of equitable selection of subjects, non-English speaking individuals may **not** be routinely excluded from research as a matter of convenience.*

In cases where the research is of therapeutic intent or is designed to investigate areas that would necessarily require certain populations who may not speak English, the researcher is required to make efforts to recruit and include non-English speaking individuals. However, there are studies in which it would be reasonable to limit subjects to those who speak English. Some examples include pilot studies, small unfunded studies with validated instruments not available in other languages, studies with numerous

questionnaires, and some non-therapeutic studies which offer no direct benefit.

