10.0 Eligibility Screening*

10.1 Describe **screening procedures** for determining subjects' eligibility.

Screening refers to determining if prospective participants meet inclusion and exclusion criteria.

Include all relevant screening documents with your submission (e.g. screening protocol, script, questionnaire).

Response: [name] is a licensed physical therapist. She will perform screening procedures for the patients. We will examine the individual's ability to ambulate 100 feet with or without assistive devices but not with the assistance of a caregiver to ensure independent walking through the protocol.

N/A: There is no screening as part of this protocol.

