of training with a cable-actuated robot will be provided. The device will augment 15% of their own body weight. While they are walking with the device, auditory feedback will be provided for the participants who are assigned to the auditory group. The auditory and non-auditory groups will be randomly assigned. Furthermore, one of the 3 different types of auditory feedback will be randomly assigned to participants from the feedback group. A break of 5 minutes will be provided after 10 minutes of walking with the device. After the robotic training is completed, the device will be taken off and the participant will walk without the device to monitor the immediate retention of the training. After every 10 minutes, the researcher will ask the participant questions as per the Borg exertion scale to check the fatigue of the participant. After finishing the treadmill session, participants will take a 10-minute break and walk 4 minutes with (or without auditory feedback) on the floor. The participant will repeat overground walking for a total of three sets. There will be a total of ten training sessions, two or three sessions a week and each session will last for a maximum of 3 hours. In addition, pre and post-training visits are required to evaluate functional gait assessment, 6-min-walk, leg strength using a dynamometer, international physical activity questionnaire (short form), usability questionnaire, and Modified Ashworth test by a physical therapist.

12.2 Describe what data will be collected.

NOTE: For studies with multiple data collection points or long-term follow up, consider the addition of a schedule or table in your response.

Response:

- We will schedule the participants to visit the lab. We will make a table when the participants are available.
- *EMG data from the muscles*
- *Vicon motion capture data*
- *Photo and Video of the test*
- *IMU sensor data*
- *Smart insole data*
- *Ground reaction force*

12.3 List any instruments or measurement tools used to collect data (e.g. questionnaire, interview guide, validated instrument, data collection form).

Include copies of these documents with your submission.

Response: Vicon motion capture system, Delsys Trigno sEMG system, and Bertec Force plate instrumented treadmill, Smart Insole

12.4 Describe any source records that will be used to collect data about subjects (e.g. school records, electronic medical records).

Response: N/A

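### Section 22.3 destroys everything held on a participant the team withdraws, even after randomisation, and does not exempt adverse-effect records

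*Combined protocol and SAP*

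**What the plan says.** The prompt for Section 22.3 asks, among other things, what happens to data already collected when a subject withdraws. The response is: "We destroy all the data and records related to the specific participant whom we withdraw from the study".

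Section 22.1 gives two triggers. The first is automatic: "If the participant has difficulties walking for 6 minutes, we will automatically withdraw the participant". The reason given is that the 6-minute walk is one of the study's metrics. The second is discretionary: "if the participant cannot follow simple instructions to walk and stop he or she may be withdrawn from the study". Neither carries a time point.

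The walking requirement at entry is different. Section 8.1 admits adults "who can ambulate a distance of 100 feet with or without the use of assistive devices", and Section 10.1 screens on the "ability to ambulate 100 feet with or without assistive devices". The 6-minute walk itself is done twice. Section 3.0 says "Before the first and after the last training, participants will be evaluated for functional gait assessment, 6-min-walk, leg strength using dynamometer", and Section 12.1 says "pre and post-training visits are required to evaluate functional gait assessment, 6-min-walk".

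On allocation, Section 12.1 says "The auditory and non-auditory groups will be randomly assigned". It does not say whether this happens before or after the pre-training visit. Section 20.2 keeps all data for at least 3 years and makes no exception for withdrawn participants.

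**The concern.** The rule can remove a randomised participant's whole record, and its main trigger is poor walking in a trial whose outcomes concern walking. Three things are at stake.

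- **Analysis of everyone randomised.** Once the records are destroyed, neither that analysis nor a sensitivity analysis for the missing participants can be done. The loss covers the motion and sEMG data, which Section 3.0 names as the primary outcomes.
- **Safety.** Section 21 has adverse effects recorded at each session on a daily report form. Nothing takes those entries out of the reach of Section 22.3.
- **Bias in improvement.** Section 19.1 names improvement from baseline to end of treatment as the major statistic. Deleting people because they walk poorly at the end can inflate it. The comparison between groups is biased in this way only if losses differ by arm, and the documents give no reason to expect that.

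**Working it through.** **Can the rule reach a randomised participant?**

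1. Entry and screening (8.1, 10.1) require 100 feet of walking. The withdrawal trigger (22.1) is difficulty walking 6 minutes. Passing the first does not exclude the second.
2. The 6-minute walk is done before the first and after the last training (3.0, 5.1, 12.1). The second occasion is necessarily after assignment. The first may be, because the order is not stated.
3. Section 22.2 pays a participant who is terminated early for hours already spent, which fits withdrawal part-way through.
4. The second trigger is not tied to any baseline test.
5. Section 22.3 has no time limit and no exception. Section 20.2 keeps all data at least 3 years. The two conflict for any withdrawn participant.

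As written, the rule does reach randomised participants.

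**How large could the distortion be?** The plan gives no withdrawal rate or dropout allowance, so there is no figure of its own to reproduce on this point. The 80% power in Section 19.2 does not enter; only that section's variance inputs are used. The number deleted and the correlations below are assumptions.

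Let *m* be the mean of the remaining standard normal values after the lowest 1, 2 or 3 are deleted (exact order statistics):

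- of 20: 0.0983, 0.1819, 0.2592
- of 10: 0.1710, 0.3175, 0.4566

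*Illustration 1: baseline-to-end improvement, all 20 participants, no true change, difficulty found at the post-training test.* Let *r* be the pre-post correlation and *c* the correlation between the outcome and the trigger. Selection shifts the post value by *c·m* and the baseline value by *r·c·m*, so the spurious change is *c*(1 − *r*)*m*, in SD units.

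| Deleted | c = 1, r = 0.5 | c = 1, r = 0.8 | c = 0.5, r = 0.5 | c = 0.5, r = 0.8 | c = 0.3, r = 0.5 | c = 0.3, r = 0.8 |
|---|---|---|---|---|---|---|
| 1 | 0.049 | 0.020 | 0.025 | 0.010 | 0.015 | 0.006 |
| 2 | 0.091 | 0.036 | 0.045 | 0.018 | 0.027 | 0.011 |
| 3 | 0.130 | 0.052 | 0.065 | 0.026 | 0.039 | 0.016 |

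A simulation with 200,000 replicates agrees for *c* = 1: 0.050, 0.091, 0.130 at *r* = 0.5 and 0.020, 0.037, 0.052 at *r* = 0.8.

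*Illustration 2: group comparison, all losses in one arm of 10.* Section 19.2 assumes 6 measures, compound symmetry with correlation 0.1, and an effect of 0.5. The SD of a subject's mean is √((1 + 5 × 0.1)/6) = √0.25 = 0.50. The bias is 0.50·*c·m*, on the scale where the planned effect is 0.5 (rounded from unrounded *m*).

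| Deleted | c = 1 (upper bound) | c = 0.5 | c = 0.3 |
|---|---|---|---|
| 1 | 0.085 | 0.043 | 0.026 |
| 2 | 0.159 | 0.079 | 0.048 |
| 3 | 0.228 | 0.114 | 0.068 |

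Simulation gives 0.085, 0.159, 0.228 for *c* = 1. Equal losses in both arms do not bias the comparison in this way.

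**The case against.** The strongest reply is that Section 22.1 is a baseline check. Its stated reason is that a participant must be able to do the 6-minute walk, which is first done before training. Session 1 then asks for a 5-minute warm-up and 20 minutes on the device with one break, so most people who cannot manage would be found early, with little data to lose. Section 23.1 handles fatigue with breaks, not withdrawal. This reading is plausible, and a case found before assignment would be only a late screen failure. But the text does not say so, and the second trigger has no link to baseline.

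On bias, Illustration 1 needs the least likely time, the final assessment. If the trigger were met at the pre-training test instead, the same model reverses sign: −(1 − *r*)*m*, about −0.05, −0.09 and −0.13 SD at *r* = 0.5 and *c* = 1. That stands, so the direction of bias depends on timing that the plan leaves open. The magnitudes also rest on assumptions and are mostly below 0.1 SD.

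On safety, neither trigger is an adverse event, and weekly meetings with the principal investigator would normally review adverse effects before any records were destroyed. That narrows the loss to the archived record but does not remove it.

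Read literally, Section 22.3 also covers signed consent forms. The Research Repository section deals with those specifically, and its 3-year wording is template instruction, so little weight goes on that point.

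The pilot purpose is no defence. Section 19.2 names feasibility and efficacy as aims, and who could not continue is itself a feasibility result.

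**Conclusion.** The concern holds and must be fixed. Followed as written, Section 22.3 can permanently erase the primary-outcome data and adverse-effect entries of a randomised participant, and it contradicts Section 20.2. With 10 per group, each such loss is 1/10 = 10% of an arm.

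Confidence in the reading of the text is high. How often this would happen is unknown. Under the stated assumptions, the spurious improvement for 1 to 3 deletions runs from 0.01 to 0.13 SD if the trigger is met at the post-training test. The bias in the group comparison is at most 0.09 to 0.23 against a planned effect of 0.5, and only if all losses fall in one arm. The severity rests on the irreversible loss of randomised and safety data, not on these illustrations.

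**What to change.** Replace the Section 22.3 response with:

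> Data collected up to withdrawal are retained, and all randomised participants are analysed in their assigned group using all available measurements; adverse-effect records are retained in every case.

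Then:

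- Handle any participant's request to delete other data as the consent form provides, and report the number of such requests by group.
- Align Section 20.2 with the new text.
- Reconcile Sections 8.1, 10.1 and 22.1 on the walking requirement, and state when it applies relative to randomisation. If a check before assignment was intended, one sentence settles it. No position is taken here on the clinical criterion for entering or continuing.

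Retention cannot supply end-of-treatment values for someone withdrawn mid-course, but the mixed-effects model in Section 19.1 can use the measurements already taken.

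The cost is a few sentences in Sections 20.2, 22.1 and 22.3, with matching wording in 8.1 and 10.1 if needed, and possibly a change to the consent form, which was not among the documents reviewed. No procedures are added.

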23.0 Risks to Subjects*

23.1 *List the reasonably foreseeable risks, discomforts, hazards, or inconveniences to the subjects related to their participation in the research. Consider physical, psychological, social, legal, and economic risks. Include a description of the probability, magnitude, duration, and reversibility of the risks.*

NOTE: Breach of confidentiality is always a risk for identifiable subject data.

Response: This research involves minimal risk to participants. Subjects will be explicitly informed the following “Some risks are unknown, so if you have experienced any shortness of breath or chest pain in the past while walking, you should not participate in this study.” Though highly unlikely, there can be fatigue by repeated walking tasks multiple times. If this is the case, the participant can request a break as much as he/she needs. Also attaching sEMG electrodes on the skin can cause mild skin irritation. Once the participant expresses discomfort, we will stop the experiment and remove the device.

23.2 *Describe procedures performed to lessen the probability or magnitude of risks, including procedures being performed to monitor subjects for safety.*

Response: Researchers who will perform this study will be trained to ask the participant if the participant feels fatigued every 10 minutes. There will be multiple emergency switches to stop the device immediately. The participant will wear a safety harness when walking with the cable-actuated robotic device.

23.3 If applicable, indicate which procedures may have risks to the subjects that are currently unforeseeable.

Response: We do not expect any risk in this experimental procedure.

23.4 If applicable, indicate which research procedures may have risks to an embryo or fetus should the subject be or become pregnant.

Response: We do not expect any risk in this experimental procedure.

23.5 If applicable, describe risks to others who are not subjects.

Response: We do not expect any risk in this experimental procedure.

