11.0 Recruitment Methods

N/A: This is a records review only, and subjects will not be recruited. NOTE: If you select this option, please make sure that all records review procedures and inclusion/exclusion screening are adequately described in other sections.

11.1 Describe when, where, and how potential subjects will be recruited.

NOTE: Recruitment refers to how you are identifying potential participants and introducing them to the study. Include specific methods you will use (e.g. searching charts for specific ICD code numbers, Research Participant Groups, posted advertisements, etc.).

Response: Extensive distribution of flyers through organizations such as WNY parent's network, UB boards that allow study flyers, clinical

facilities in the greater Buffalo region, and clinicians that see patients with CP. The Buffalo Research Registry (BRR) is a database of people from Buffalo and Western New York who have shown interest in becoming research study volunteers. We will ask for a list of potential participants from the BRR. A flyer providing information on the study will be emailed or mailed to potential participants from this list.

11.2 Describe how you will protect the privacy interests of prospective subjects during the recruitment process.

NOTE: Privacy refers to an individual's right to control access to him or herself.

Response: Participants will self-select to respond to one of the flyers for the study. They need to choose to contact the researchers to participate in the study. The settings for the phone conversation and data collection will be private areas. *The researcher will emphasize that participation in this study is voluntary and subjects may withdraw at any time with no consequences.*

11.3 Identify any materials that will be used to recruit subjects.

NOTE: Examples include scripts for telephone calls, in person announcements / presentations, email invitations.

 *For advertisements, include the final copy of printed advertisements with your submission. When advertisements are taped for broadcast, attach the final audio/video tape. NOTE: You may submit the wording of the advertisement prior to taping to ensure there will be no IRB-required revisions, provided the IRB also reviews and approves the final version.*

Response: *Flyers and follow-up phone conversations when participants demonstrate an interest in the study.*

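### Section 23.1 says people with past chest pain or breathlessness on walking should stay out of the study, but the 8.2 exclusions do not list that history, so in the protocol sections the restriction rests on self-exclusion

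*Combined protocol and SAP*

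**What the plan says.** **The warning.** Section 23.1 introduces a statement with "Subjects will be explicitly informed the following" and then gives its content: "if you have experienced any shortness of breath or chest pain in the past while walking, you should not participate in this study". The sentence is in the passive and does not say who delivers it or when.

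**The exclusion list.** Section 8.2 covers foot and knee deformity, recent surgery, pregnancy, lower limb prosthetics, seizure disorder, severe arthritis, and "severe respiratory problems such as chronic obstructive pulmonary disease, heart disease, a loss of sensation, uncontrolled blood pressure". No item refers to symptoms during walking.

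**Screening.** The form text in 10.1 defines screening as establishing whether prospective participants meet the inclusion and exclusion criteria. The response says of a licensed physical therapist, "She will perform screening procedures for the patients". The one check it goes on to describe is the "ability to ambulate 100 feet with or without assistive devices but not with the assistance of a caregiver".

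**Recruitment contact.** Section 11.3 mentions flyers and "follow-up phone conversations when participants demonstrate an interest in the study". The content of the calls is not given.

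**Safeguards after entry.** Every 10 minutes the researcher asks "questions as per the Borg exertion scale to check the fatigue of the participant" (12.1), and under 23.2 researchers are "trained to ask the participant if the participant feels fatigued every 10 minutes". Adverse effects are asked about after each session, and a physical therapist watches the walking pattern (21.1). Difficulty walking for 6 minutes leads to automatic withdrawal (22.1). The experiment stops when a participant expresses discomfort (23.1).

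**The concern.** The protocol's authors have judged that people with a certain symptom history should not take part, and have placed that judgement in the risk section as advice to the subject. The list that decides eligibility does not carry it. The two groups are not the same: a person may have had chest pain or breathlessness on walking and never been given a cardiac or severe respiratory diagnosis.

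Someone who screens to section 8 as written can therefore enrol a person whom 23.1 says should stay out, if that person hears the warning and carries on. That participant would then walk on a treadmill against a downward force. What is missing is a listed criterion to screen against and a record that the history was considered. This is a question of participant safety and of consistent eligibility, not of inference.

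**Working it through.** The plan gives no figure to reproduce here. The check is mainly a comparison of sections, followed by simple arithmetic on exposure.

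**1. Compare the restriction with the criteria.**

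| Person | Told by 23.1 not to participate | Excluded by 8.2 |
|---|---|---|
| Heart disease, with chest pain on walking | Yes | Yes |
| Severe respiratory problem, breathless on walking | Yes | Yes |
| Chest pain on walking, no diagnosis | Yes | No |
| Breathless on walking, mild or undiagnosed respiratory problem | Yes | No |

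The last two rows are the gap.

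**2. Look for another route to exclusion before entry.** By its own definition, screening in 10.1 reaches only what section 8 lists. The described 100-foot walk tests independent walking. It is 100 × 0.3048 = 30.5 m. At assumed speeds of 0.4 to 1.2 m/s it lasts 30.5/0.4 = 76 s down to 30.5/1.2 = 25 s. The speeds are assumptions, not protocol figures. A walk that short is unlikely to stand in for a question about symptoms on longer walking. Sections 11.1 to 11.3 describe no symptom question.

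**3. Look for a route after entry.** Section 22.1 names two grounds for withdrawal without consent: difficulty with 6 minutes of walking, and inability to follow simple instructions. Neither is symptom history. The prompts in 12.1 and 23.2 concern exertion and fatigue, and the adverse-effect question in 21.1 follows the session. These steps may detect symptoms as they occur. None asks about the past.

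**4. Size the exposure.** Inputs: about 20 minutes of device walking per session (5.1, 12.1); at most 10 sessions (5.1); a 5-minute break after 10 minutes with the device (12.1); 15% body-weight augmentation (12.1).

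- Device walking per participant: 10 × 20 = 200 minutes at most, spread over sessions held two or three times a week.
- Longest scheduled device bout: about 10 minutes, because the break splits the 20.
- Relative to the pre-training 6-minute walk: 10/6 = 1.7.

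The 6-minute walk is thus a useful partial test. It is somewhat shorter than a device bout and is not described as being done with the device.

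**5. Effect on the statistics.** None. The sample size of 20, the power statement in 19.2 and the analysis in 19.1 do not depend on this criterion.

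**The case against.** The strongest reply concerns section 10.1. It describes no check for any 8.2 exclusion, not for heart disease, seizures, pregnancy or surgery, yet those plainly apply. It is therefore not a full account of what the therapist does. The form also asks for screening documents to be submitted separately. The warning is worded to the subject, which suggests consent or script text, and neither consent pages nor phone scripts were available. All of this stands. A reader might infer that nobody asks about these symptoms; the documents do not support that, and silence in 10.1 is not evidence for it. The point rests on the mismatch between 8.2 and 23.1.

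Three other stronger readings also fail:

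- **That the sections contradict each other.** They can be followed together; one is narrower than the other.
- **That staff would have no written basis for refusing someone who discloses the history.** The sentence in 23.1 is a basis of a kind. What is absent is a listed criterion.
- **That device exposure should be compared with the 6-minute walk as 20 minutes to 6.** The scheduled break rules that out.

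It is also fair to say that a person who hides the history after the warning could hide it from a direct question. The gain lies with those who would not act on a general warning but would answer a question truthfully.

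Finally, a fixed exclusion removes clinical judgement. Section 4.1 describes early decline in endurance among adults with CP, so any past breathlessness on walking, read literally, could cover a meaningful share of candidates. That is an objection to the breadth of the wording in 23.1 as much as to the fix. It is no reason to leave the two sections different.

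**Conclusion.** The concern holds in limited form. The exclusion list falls short of the protocol's own safety restriction, and in the sections reviewed that restriction depends on self-exclusion. It should be corrected, though it is not a critical flaw.

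The affected group is people with the symptom history and no 8.2 diagnosis. The documents give no frequency for them, so no probability of harm is claimed. Exposure is bounded at 200 minutes of device walking per participant, in scheduled bouts of about 10 minutes. The 6-minute walk, Borg ratings, therapist monitoring and stopping on discomfort already cover part of the risk.

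The conclusion assumes that no unseen screening form, phone script or consent page makes the history an eligibility criterion. If one already asks the question, the remaining need is the line in 8.2 and a reference to that document in 10.1.

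**What to change.** Two changes:

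1. In 8.2, add a history of chest pain or shortness of breath while walking to the exclusions, so that the list matches 23.1.
2. In 10.1, state that the screening physical therapist asks about this history directly and records the answer before any treadmill or device walking.

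Keep the 23.1 warning and all the existing safeguards. If the sponsor considers the wording too broad for adults with CP, narrow it in 23.1 and 8.2 together.

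The cost is one line and one recorded question, asked by someone who already screens. Extra screen failures are possible in a study of 20. Section 7.2 gives no expected screening number, so how many cannot be stated; they would be limited to people whom 23.1 already says should not take part.
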